5.7.2 Phase 1 – Run-in-Period

Rociletinib monotherapy will be administered orally BID during the 7-day Run-in-Period. Dose reductions of rociletinib during the Run-in-Period are not allowed for reasons other than a DLT. Dose delays of rociletinib for up to 48 hours for toxicity management is allowed. Any patient who experiences an AE(s) that requires either a delay of treatment for more than a total of 48 hours or a dose reduction during the 7-day Run-in Period of rociletinib monotherapy will not be eligible for combination therapy. Such a patient will only receive monotherapy rociletinib for the duration of participation in the study.

5.7.3 Phase 1 – Cycle 1

The first dose of MPDL3280A at 1200 mg will be administered by IV on C1D1. Dose reductions of rociletinib are not allowed for reasons other than a DLT or a decision by the CSC based on emerging safety data. Dose delays of rociletinib are not allowed for reasons other than toxicity. Patients are eligible for safety and DLT evaluation of the cohort if they receive at least 75% of the planned total dose of each study drug within Cycle 1 or they experience a DLT at any time during Cycle 1.

5.7.4 Beyond DLT Assessment (Phase 1 – Cycle 2+ and Phase 2 – All Cycles)

For patients who experience a toxicity that is equivalent to a DLT – If the toxicity is assessed as being related to rociletinib, the next dose of rociletinib should be held until resolution of the toxicity to Grade 1 or to the baseline level (if severity > Grade 1 at baseline) and then reduced to the next dose level of rociletinib (Table 7), unless permanent discontinuation of rociletinib is required per toxicity management guidelines of the protocol (Sections 6.1 and 6.3). If the toxicity is assessed as being related to MPDL3280A, the next dose of MPDL3280A should be held until the toxicity has resolved to Grade 1 or to the baseline level (if severity > Grade 1 at baseline), unless permanent discontinuation of MPDL3280A is required per toxicity management guidelines of the protocol (Sections 6.2 and 6.3). In addition, because there is no available antidote for MPDL3280A and discontinuation of MPDL3280A may not have immediate therapeutic effect, consideration may be given to holding rociletinib doses temporarily even if the toxicity is not attributed to rociletinib.

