6.1 Rociletinib Expected or Potential Toxicities

6.1.1 Management of Prolonged QTc

Electrocardiograms will be performed throughout the study as described (see Table 1 and Section 8.4.2.4). Readings for QTc prolongation will be based on the average for the triplicate ECGs for each time point. Patients are required to have within-normal-range potassium and magnesium at enrollment, and these electrolytes should be maintained within range during rociletinib treatment, using supplementation if necessary.

Guidelines for dose modification and stopping criteria due to QTc prolongation are provided in Table 9.

QTc-Prolongation ^a	Action and Dose Modification
$QTcF \ge 501$ msec on at least two	• Interrupt study treatment until QTcF prolongation resolves to Grade 1 (QTcF > 450-480 msec) or baseline;
separate ECGs ^a (Grade 3)	• Test serum potassium, calcium, phosphorus and magnesium. If abnormal, correct per routine clinical practice to within normal limits;
	• Review concomitant medication usage for a prolonged QTc;
	• Restart at a reduced dose level ^b ;
	• If Grade 3 QTc prolongation recurs after 2 dose reductions, permanently discontinue study treatment ^b ;
	 If Grade 4 QTc prolongation (QTcF ≥ 501 or 60 msec increase from baseline and polymorphic ventricular tachycardia or serious arrythmia) occurs, permanently discontinue study treatment^b

 Table 9:
 Withholding and Stopping Criteria for QTc-Prolongation

msec, milliseconds; QTcF, QT interval on electrocardiogram corrected using Fridericia's formula (see Appendix D) ^a Based on average QTc value of triplicate ECGs.

^b If the QTc prolongation resolves to Grade 1 or baseline, the patient may resume study treatment if the Investigator and Medical Monitor agree that the patient will benefit from further treatment.

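### Table 9 orders a permanent stop for two QTc events, but footnote b on the same two lines lets the patient resume, and nothing says which governs

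*Combined protocol and SAP*

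**What the plan says.** All of the conflicting text is in Section 6.1.1, Table 9, of the combined protocol and SAP. After a Grade 3 event, treatment is interrupted, electrolytes and concomitant medication are reviewed, and the patient restarts: "Restart at a reduced dose level ^b". Two further lines set permanent stops.

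- Recurrent Grade 3: "If Grade 3 QTc prolongation recurs after 2 dose reductions, permanently discontinue study treatment ^b".
- Grade 4, which requires an arrhythmia as well as the prolongation: "polymorphic ventricular tachycardia or serious arrythmia) occurs, permanently discontinue study treatment^b".

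Marker b is on the restart line and on both permanent-stop lines. The footnote's first condition is recovery of the QTc prolongation to baseline or Grade 1. Its second condition, joint agreement on benefit, is in the permission itself: "the patient may resume study treatment if the Investigator and Medical Monitor agree that the patient will benefit from further treatment".

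Section 5.7.4 tells sites to hold rociletinib and then reduce it for a DLT-equivalent toxicity attributed to it, "unless permanent discontinuation of rociletinib is required per toxicity management guidelines of the protocol (Sections 6.1 and 6.3"). It therefore sends the reader back to Table 9 to learn when a stop is mandatory.

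**The concern.** A stop that can be lifted when the event resolves is a hold, not a permanent discontinuation. On the restart line footnote b fits, because that line already contemplates resumption. On the other two lines it reverses the instruction it is attached to.

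Two things are at stake. The first is patient handling. Two sites reading the same page could treat the same serious event differently, one ending treatment for good and the other seeking agreement to resume, and each could claim to have followed the protocol.

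The second is classification. Section 9.7.3 records temporary interruption and permanent discontinuation as separate actions. Section 10.2.5.2 puts AEs leading to discontinuation and AEs leading to interruption or reduction in separate tables. Section 10.2.2 summarises the primary reason for discontinuation. A patient stopped under one of these lines and later resumed under the footnote could be entered in either category.

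**Working it through.** The point concerns wording, so there is no statistical figure to reproduce. The check sets the relevant places side by side.

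| Place | What it requires | Marker b? | Effect of footnote b |
|---|---|---|---|
| Table 9, restart line | Restart after Grade 3 at a lower dose level | Yes | Consistent: adds a condition to a restart |
| Table 9, recurrent Grade 3 line | Permanent stop if Grade 3 recurs after 2 dose reductions | Yes | Reverses the line |
| Table 9, Grade 4 line | Permanent stop | Yes | Reverses the line |
| Section 5.7.4 | Hold and reduce, unless Section 6.1 or 6.3 requires a permanent stop | Not applicable | Depends on Table 9 for the answer |
| Section 11.1 | List of criteria for stopping all treatment | Not applicable | No QTc-specific criterion |

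**Step 1: do line and footnote address the same event?** Yes. The marker is on the line itself, and the footnote speaks of the QTc prolongation without limiting itself to a first Grade 3 event.

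**Step 2: does another section break the tie?** No. Section 5.7.4 defers to Section 6.1. Section 11.1 is silent on QTc. Its general criterion, an event that the Investigator judges an unacceptable safety risk, leaves the matter to judgement.

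**Step 3: does the protocol use the same language elsewhere with a right to resume?** The permanent-discontinuation instructions in Sections 6.2 and 6.3 carry no footnote of this kind. Table 9 therefore gives the same instruction a different meaning.

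**Step 4: does the footnote define what resumption means?** It names no dose. By Table 7, two reductions from 500 mg BID run 500 to 375 to 250 mg BID, and Section 5.7.1.1 allows nothing below 250 mg. A patient who started at 500 mg BID and meets the recurrent Grade 3 trigger is already at that floor, so the table's restart line, which calls for a lower level, cannot be followed. The documents do not say what would apply instead.

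**Count:** marker b is on three lines. It fits one and contradicts two, and those two are all of Table 9's permanent-stop triggers.

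**The case against.** The best case for the plan is that footnote b is a deliberate exception: stop, unless the prolongation has resolved and both the Investigator and the Medical Monitor agree on benefit. Placing the marker on three separate lines looks intended. The protocol also uses a default with an override elsewhere: Sections 5.7.4 and 11.1 require discontinuation after an over-long dose hold unless the Medical Monitor gives permission. This reading is possible, so a reader who infers that line and footnote are beyond any reconciliation goes too far. But those sections state the exception openly in the rule, whereas Table 9 calls the stop permanent and undoes it in a footnote. If an exception is meant, the line should say so.

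Three further inferences are tempting and are not supported.

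- **That a site could resume treatment on its own.** Footnote b requires two-party agreement, and Section 11.1 separately requires a stop for unacceptable safety risk. These safeguards reduce the risk. They rest on judgement and do not settle which text governs.
- **That the 10 patients with QTcF above 500 msec in Section 1.3.1 measure the problem.** They come from the earlier monotherapy study, with HBr doses up to 1000 mg BID. A value in that range corresponds to Table 9's Grade 3 threshold; Grade 4 also needs polymorphic ventricular tachycardia or a serious arrhythmia, and Section 1.3.1 describes no such case. Table 4 shows treatment-related QT prolongation in 0 of 18 patients at 500 mg BID HBr, the higher of the two planned cohort doses. Eighteen is few, and Section 3.2.2 lets the CSC evaluate other doses, so the risk is not excluded either.
- **That discontinuation records are bound to be inconsistent.** Section 9.7.3 records the action actually taken, so a patient who resumes can be coded as interrupted. Inconsistency is possible, not certain.

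**Conclusion.** The contradiction stands. Both permanent-stop lines in Table 9 carry a footnote permitting resumption, and no other section says which prevails. It is an internal contradiction in a stopping rule for a serious cardiac event, not a debatable design choice, and it should be corrected because it bears on patient safety.

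Its scope is narrow. A reader might take the Grade 3 trigger to be any recurrence, but Table 9 limits it to recurrence after 2 dose reductions. A reader might also take resumption to follow automatically from recovery, but the footnote requires agreement as well. The number of patients likely to reach either trigger is not given and cannot be derived from the documents. Sample size, power and error rates are unaffected. The conclusion rests only on the position of marker b, which appears on all three lines, and on the footnote, which reads as complete.

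**What to change.** The sponsor should state which Table 9 lines footnote b applies to and make the two permanent-stop lines and the footnote agree. If resumption is meant to be possible after either event, the line itself should say so, and what resumption means should be reconciled with Table 7 and Section 5.7.1.1. If it is not, the marker should come off those lines. This review takes no position on which clinical rule is right.

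Once that is settled, a sentence in Section 9.7.3 or 10.2.5.2 should say how a patient who stops and later resumes is classified. The cost is footnote placement and a few words. No design parameter changes.

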6.1.2 Management of Hyperglycemia

Rociletinib causes hyperglycemia in some people. Clinical experience with rociletinib suggests hyperglycemia generally occurs within the first 3 weeks of treatment, leading to the need for more intensive glucose monitoring during the first several weeks of the study in order to minimize the risk of symptomatic hyperglycemia. Because later onset of hyperglycemia is also possible with rociletinib treatment, regular monitoring of glucose and of symptoms of hyperglycemia will be required through the end of rociletinib treatment.

Fasting blood glucose (FBG) will be measured by local laboratories for the following visits: Screening/Baseline visit, Day 1 of the Run-in-Period (Phase 1 only), C1D1, C1D4, C1D8, C1D15, Day 1 of each cycle beginning with Cycle 2, and at the EOT Visit (Table 1). Investigators should use discretion on an individual-patient basis to determine the need for more frequent monitoring.

Diabetes and glucose intolerance are not contraindications to the use of rociletinib. Patients with pre-existing diabetes may require more frequent glucose monitoring and/or adjustments of diabetic medication. In addition to the scheduled local laboratory tests for FBG (see Table 1), patients with pre-existing diabetes should perform home monitoring at least once weekly (if not more frequently).

For patients who are not already monitoring their glucose levels, sites are strongly encouraged to implement *patient home monitoring of fasting urine glucose for Cycle 1 and Cycle 2*. If preferred, home monitoring of blood glucose is also acceptable. Patients should be educated to contact the site if they have any positive urine glucose test or a home blood glucose reading of > 160 mg/dL (> 8.9 mmol/L) and any time they experience symptoms that have correlated with rociletinib-induced hyperglycemia, including increases in nausea, vomiting, anorexia, diarrhea, and/or fatigue. Symptoms more commonly associated with diabetes, such as polydipsia, polyuria, and polyphagia, rarely occur with rociletinib-induced hyperglycemia. Upon reports of positive home tests and/or symptoms suggesting hyperglycemia, local laboratory FBG tests should be performed.

Guidelines for management of hyperglycemia, based on the results of laboratory FBG values and patient symptoms, are presented in Table 10. Sites are encouraged to follow these guidelines, although management of individual patients may be influenced by local practices and the treating physician's judgment.

FBG Result	Antihyperglycemic Intervention ^a	Rociletinib Dose Modification
Grade 2 (> 160 to 250 mg/dL; > 8.9 to 13.9 mmol/L)	• If asymptomatic, ^b repeat test within 1 week; if results in this range at least twice in 1 week, start antihyperglycemic ^c and continue home monitoring;	• Rociletinib may continue without interruption or dose reduction
	• If symptomatic, ^b start antihyperglycemic and continue home monitoring.	
Grade 3 (> 250 to 500 mg/dL;	• Start antihyperglycemic and continue home monitoring.	• If asymptomatic, ^b rociletinib may continue without interruption or dose reduction;
> 13.9 to 27.8 mmol/L)		• If symptomatic, ^b interrupt rociletinib until resolution/improvement in symptoms and FBG < 250 mg/dL (< 13.9 mmol/L) ^c .
Grade 4 (> 500 mg/dL; > 27.8 mmol/L)	 Start antihyperglycemic and continue home monitoring. Consider adding a second antihyperglycemic agent.^d 	 Interrupt rociletinib dosing until resolution/improvement in symptoms and FBG < 250 mg/dL (< 13.9 mmol/L).^c

Table 10: Management Guidelines for Hyperglycemia

FBG, fasting blood glucose

^a Oral antihyperglycemic agent (eg, metformin), which may need to be maintained for duration of rociletinib treatment. Use of insulin or agents which increase insulin production (eg, sulphonyl ureas) is generally not recommended because the mechanism of rociletinib-induced hyperglycemia is not due to a deficit in insulin production.

^b Increased nausea, vomiting, anorexia, diarrhea, and fatigue have been most common symptoms of hyperglycemia.

^c Per Investigator discretion, rociletinib may be restarted at the same dose. A reduced dose may also be considered if glucose levels prove difficult to control.

^d Additional antihyperglycemia agents such as SGLT2 inhibitors (eg, dapagliflozin) or pioglitazone, which increase glucose uptake or increase glucose excretion, may be added to metformin.

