HIV/HBV/HCV serology ^R	Х							
ECHO/MUGA ^s	Х							
12-lead ECG ^T	\mathbf{X}^{F}	Х	X	X	X	X	X	
Pulmonary function test ^U	X							

			Treatment Period					
	Screening Period	Rociletinib 7-day Run- In- Period (Phase 1 only)	Cycle 1 combination therapy (21-day cycle) Cycle 2+ combination therapy (21-day cycle)			Cycle 2+ combination therapy (21-day cycle)	End of Treatment ^C	Follow Up
Procedure ^A	Day -28 to Day 0	Day 1 ^B	Day 1 ^B	Day 4	Days 8 and 15 ±2 days	Day 1 ±3 days		
Tumor biopsy ^V	Х						X ^{C,V}	
Tumor assessments ^W	Х					Х	$\mathbf{X}^{\mathrm{C},\mathrm{W}}$	
Pharmacogenomic blood sample (predose)		Х	X (Phase 2 only)					
Rociletinib PK sampling ^X		Х	Х		Days 8-9	X (see Table 2)	X ^{C,X}	
MPDL3280A PK sampling ^x			X			X (see Table 2)	X ^{C,X}	Х
ATA testing ^X			Х			X (see Table 2)	X ^{C,X}	Х
TBNK blood sample ^X	X ^F		Х		X		X ^{C,X}	
Pharmacodynamic blood sample ^X	Х		X		Day 8	X (see Table 2)	X ^{C,X}	
Dispense rociletinib/ drug accountability/diary ^Y		Х	X			Х		
Rociletinib in-clinic administration ^Y		Х	X		Day 8	Х		
MPDL3280A administration ^Z			X			Х		
Adverse events ^{AA}	Х	Х	Х	Х	X	Х	Х	
Concomitant medications ^{BB}	X	Х	X	X	X	Х	X	
Survival assessment/ subsequent therapies ^{CC}							Х	X

ATA, anti-therapeutic antibody; ECG, electrocardiogram; ECOG, Eastern Cooperative Oncology Group; EGFR, epidermal growth factor receptor; HBV, hepatitis B virus; HCV, hepatitis C virus; HIV, human immunodeficiency virus; MUGA, multigated acquisition (scan); PK, pharmacokinetic; TBNK, T, B, and natural killer; TSH, thyroid-stimulating hormone.

А	Unless otherwise specified: Clinic visits for the specified assessments in Cycle $2+$ should be completed ± 3 days of the scheduled time point relative to C1D1.
	Assessments are to be performed prior to administration of study treatment, when applicable. All results must be reviewed by the Investigator prior to administration
	of study treatment. Perform assessments as scheduled on C1D4 (ie, no window) and assessments for C1D8 and C1D15 within ± 2 days of the scheduled time points.
В	Procedures required on Day 1 of Run-in-Period (Phase 1) or CIDI (Phase 2) may be omitted if completed < 3 days earlier during the Screening Period.
С	Patients will be asked to return to the clinic 28 days (+7 days) after the last dose of study treatment, or before the patient initiates another anticancer agent, if sooner,

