1.3.1 Safety of Rociletinib from Clinical Studies

Preliminary safety data are presented for the ongoing CO-1686-008 and completed CO-1686-016 studies. As of 04 June 2014, 190 patients have received at least one dose of rociletinib: 42 healthy male volunteers (Study CO-1686-016) and 148 patients with advanced NSCLC (Study CO-1686-008). The overall safety data presented here are for NSCLC patients who received rociletinib in Study CO-1686-008.

Study CO-1686-008

Preliminary safety data are reported for 148 patients with advanced NSCLC in this study, including 57 patients who were treated with rociletinib free base at total daily doses ranging from 150 mg up to 1800 mg (once daily [QD], BID, and three times daily [TID] dosing schedules) and 91 patients who were treated with rociletinib HBr at total daily doses ranging from 1000 mg to 2000 mg (500 mg BID, 625 mg BID, 750 mg BID and 1000 mg BID). Rociletinib HBr is being studied in ongoing clinical studies and will be used in this study (Section 5.1).

Dose-Limiting Toxicities: Enrollment of patients to the dose escalation phase was completed in February 2014 with a DLT rate of < 33% at all evaluated doses. The DLT evaluable population included all patients who had completed Cycle 1, and who were enrolled while the dose escalation part of the study was ongoing. The most frequently reported DLT was hyperglycemia/glucose tolerance impaired which occurred at a similar frequency (11% to 25%) across all rociletinib dose levels with the rociletinib HBr formulation (500 mg BID, 625 mg BID, 750 mg BID, and 1000 mg BID). Hyperglycemia can be effectively managed with the addition of anti-hyperglycemic therapy and/or dose reductions. Guidance for the management of hyperglycemia associated with rociletinib treatment is provided in Section 6.1.2.

Serious Adverse Events (SAEs) and Deaths: A total of 43 patients experienced at least one SAE, and among these, 17 patients (11.5%) had an SAE assessed as related to study drug. The most commonly reported treatment-related SAE was hyperglycemia (reported by 6% of patients). Four patients (3%) experienced an SAE of vomiting, and 3 patients (2%) experienced

an SAE of nausea. All other treatment-related SAEs occurred in 2 or fewer patients. Treatment-related SAEs are summarized in Table 3.

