3.2 Dose Finding Phase (Phase 1)

The Dose Finding Phase will be conducted with patients who have progressed after at least 12 weeks of treatment with a prior first- or second-generation EGFR TKI (ie, erlotinib, gefitinib, afatanib), regardless of T790M mutation status. The Dose Finding Phase will be used to determine the MTD or MAD and RP2D of the combination of rociletinib and MPDL3280A, and to evaluate the safety, tolerability, and PK profile of the combination treatment. The Dose Finding Phase will include a 7-day Run-in-Period of rociletinib monotherapy prior to the initiation of combination treatment. Patients will receive daily oral BID doses of rociletinib at the Dosing Cohort-defined dose level (Section 3.2.2). Patients who experience an AE that requires a reduction or more than 48-hour delay in dose of rociletinib during the Run-in-Period will not go on to receive the combination of rociletinib and MPDL3280A, but will remain on study to receive rociletinib monotherapy; an additional patient will be enrolled as a replacement for inclusion in the same Dosing Cohort.

For the Dose Finding Phase, Cycle 1 will begin with the initiation of combination treatment following a successful completion of the Run-in-Period and will be used for the determination of DLTs. Patients will continue to receive daily oral BID doses of rociletinib (at the Dosing Cohort-defined dose level) and IV doses of MPDL3280A on Day 1 of each cycle, in consecutive 21-day cycles. Thereafter, treatment and monitoring of patients will be conducted in 21-day treatment cycles. Patients will be evaluated regularly for safety, PK, efficacy and pharmacodynamics according to the Schedule of Assessments (see Table 1). For further details on the planned assessments and analyses of safety, PK, efficacy and pharmacodynamics, please refer to Sections 8.4.2-8.4.5.

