3.4 Study Conduct and Duration of Patient Follow-Up

The study will comprise a Screening Period, and Treatment Period, and a Follow-up Period as outlined in Table 6. Please refer to Section 8 for additional details.

	Sign ICF						
COFFNINC DEDIOD	Screening Assessments						
SCREENING PERIOD	Up to 28 days before 1st dose of study drug (biops	sy within 60 days pi	rior)				
	Enrollment						
	Study assessments every 21 days. Additional ECG and glucose		Day 1				
TREATMENT PERIOD	monitoring during Cycle 1 (Day 4, Day 8, and Day 15). Tumor	Cycle 1	Day 4				
Oral rociletinib BID + IV	assessments every 2 cycles through Cycle 6 (end of Cycles 2, 4, and 6): every 3 cycles after Cycle 6 (end of Cycles 9, 12, etc.); and	Cycle I	Day 8				
MPDL3280A every 21days	at the EOT Visit. The frequency of tumor assessments may be		Day15				
	reduced after 2 years with approval of Medical Monitor.	Cycle 2 +	Day 1				
		Ļ					
	Disease Progression	Rociletinib and	/or MPDL3280A				
		treatment post-progression (Spons					
	(Optional post-progression tumor biopsy)	approval) with con	rotocol				
		↓ .					
	Treatment discontinuation						
END OF STUDY PERIOD	Follow-up Safety Assessment						
	28 days after last dose of study drug (rociletinib or MPDL3280A)						
	PK/ATA blood samples 120 days after last dose of MPDL3280A (see Table 2)						
	Follow-up for subsequent anticancer therap	vies and survival					
	Every 12 weeks						

Table 6:Study Schematic (CO-1686-032)

ATA, anti-therapeutic antibody; BID, twice-daily; ICF, informed consent form; IV, intravenous; PK, pharmacokinetics

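### In Phase 1 the recommended home glucose monitoring begins a week after rociletinib does, so patients not already self-monitoring have no routine glucose check recommended on drug Days 2–7

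*Combined protocol and SAP*

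**What the plan says.** Section 6.1.2 gives the reason for early monitoring: "hyperglycemia generally occurs within the first 3 weeks of treatment, leading to the need for more intensive glucose monitoring". Its stated purpose is to keep symptomatic hyperglycemia to a minimum.

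Two routine measures follow.

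- **Laboratory fasting glucose.** The early visits are "Screening/Baseline visit, Day 1 of the Run-in-Period (Phase 1 only), C1D1, C1D4, C1D8, C1D15". Day 1 of each later cycle and the End of Treatment visit come after these. Table 6 (Section 3.4) likewise attaches the extra glucose checks to Cycle 1.
- **Home testing.** For patients who do not already test, sites are encouraged to arrange "patient home monitoring of fasting urine glucose for Cycle 1 and Cycle 2"; home blood glucose is an accepted alternative. No frequency is given. Patients with pre-existing diabetes are asked to test at home at least weekly.

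Two safeguards are not tied to a cycle. Investigators may test more often at their discretion, and there is a trigger rule: "Upon reports of positive home tests and/or symptoms suggesting hyperglycemia, local laboratory FBG tests should be performed".

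On timing, Section 3.2 states that in the Dose Finding Phase "Cycle 1 will begin with the initiation of combination treatment", after 7 days of rociletinib alone. Phase 2 has no run-in, so rociletinib starts on C1D1 (Section 3.3).

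**The concern.** The risk period is counted from the start of rociletinib, but the home-testing recommendation is counted in cycles. The two clocks agree in Phase 2. In Phase 1 they differ by 7 days, and the protocol gives no reason for treating the phases differently. The wording reads as if written for a schedule without a run-in.

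What is at stake is detection of a common toxicity in the first of the three weeks the protocol singles out. A patient with asymptomatic hyperglycemia in that week would normally be found only at C1D1. The run-in also has its own consequence: an adverse event that needs a rociletinib dose reduction or a hold of more than 48 hours bars the patient from the combination (Sections 3.2 and 5.7.2). Finding a raised glucose before it becomes symptomatic allows oral treatment to start sooner.

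**Working it through.** The protocol states no figure to reproduce; the check is a day count.

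**Inputs.** Run-in of 7 days, Phase 1 only (Section 3.2); cycle length 21 days; laboratory glucose visits from Section 6.1.2 and Table 1; home-testing window of Cycles 1 and 2 (Section 6.1.2); risk period of drug Days 1–21 (Section 6.1.2). Table 1, footnote A: "Assessments are to be performed prior to administration of study treatment, when applicable". The Run-in Day 1 glucose is therefore a baseline value.

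**Conversion.** Phase 1: drug day = cycle day + 7. Phase 2: drug day = cycle day.

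| | Phase 1 | Phase 2 |
|---|---|---|
| Pre-dose glucose | Day 1 (Run-in Day 1) | Day 1 (C1D1) |
| Next laboratory glucose, by drug day | 8, 11, 15, 22 | 4, 8, 15, 22 |
| Intervals between laboratory checks (days) | 7, 3, 4, 7 | 3, 4, 7, 7 |
| On-drug laboratory checks in Days 2–21 | 3 (Days 8, 11, 15) | 3 (Days 4, 8, 15) |
| Recommended home window | Days 8–49 | Days 1–42 |
| Part of Days 1–21 inside the home window | 21 − 7 = 14 of 21 | 21 of 21 |
| Days 2–21 outside both the home window and the laboratory schedule | Days 2–7 | none |

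Visit tolerances are ignored (±2 days at C1D8 and C1D15, ±3 days from Cycle 2). They do not touch Days 2–7.

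**Who is affected.** Phase 1 enrolls at most 18 (Section 3.2.2). Run-in failures are replaced, which can add patients exposed to the run-in. Patients already self-monitoring come off the count, as do any of the up to 6 safety-expansion patients dosed without a run-in (Section 3.2.3).

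**Background frequency in the single-agent study CO-1686-008.**

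- Treatment-related hyperglycemia reported as an SAE (Table 3): 4/18 = 22% at the 500 mg BID HBr starting dose, exact 95% CI 6% to 48%. Across HBr doses: (4 + 1 + 2 + 1)/(18 + 17 + 50 + 6) = 8/91 = 8.8%.
- Treatment-related hyperglycemia of any grade (Table 4): 11/18 = 61% at 500 mg BID, exact 95% CI 36% to 83%. Across HBr doses: (11 + 10 + 14 + 4)/91 = 39/91 = 42.9%.
- As a dose-limiting toxicity (Section 1.3.1): "hyperglycemia/glucose tolerance impaired which occurred at a similar frequency (11% to 25%) across all rociletinib dose levels", with the HBr formulation.

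None of these figures is broken down by week of onset.

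**After the change.** A home window from the first dose covers drug Days 1–49 in Phase 1, which is 21 of the first 21 days.

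**The case against.** The strongest reply is that the gap is small and partly covered. Section 6.1.2 asks for closer monitoring early in the study, which in Phase 1 includes the run-in, and naming Cycles 1 and 2 does not forbid earlier home testing. Symptoms prompt a laboratory test at any time. What is left is asymptomatic hyperglycemia, found at most 6 days late (Day 2 to Day 8). Table 10 lets rociletinib continue unchanged in asymptomatic Grade 2 and Grade 3 cases, so dosing would change only for Grade 4. The C1D1 result must also be reviewed before study treatment is given that day, which puts detection ahead of the first MPDL3280A infusion.

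Much of this stands, and it keeps the point minor. It does not close the gap. A symptom trigger acts only once the outcome the section wants to avoid has occurred. The symptoms listed, such as nausea, anorexia and fatigue, are non-specific. Asymptomatic Grade 3 still calls for oral treatment, which would start later.

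A reader might also infer more than the documents support:

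- *That Phase 1 has fewer laboratory checks.* It does not; both phases have three on-drug checks in Days 2–21.
- *That the 14 versus 21 days measure tests done or missed.* Home testing is only encouraged and has no stated frequency, so full coverage in Phase 2 is not guaranteed either.
- *That 22% of Phase 1 patients would have a serious event in the run-in.* The 4/18 is the highest of the dose columns, covers the whole reporting period and must be read beside 8/91.
- *That DLT assessment or an endpoint is compromised.* Nothing in the documents shows this.

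**Conclusion.** The point holds as a gap in a recommendation. For Phase 1 patients who do not already self-monitor, following the protocol as written leaves drug Days 2–7 without a routine glucose check, inside the 3-week period the protocol itself names. The recommended home window reaches 14 of the first 21 drug days in Phase 1 against 21 of 21 in Phase 2.

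This rests on reading Cycles 1 and 2 literally, with C1D1 on drug Day 8, and on the Run-in Day 1 sample being taken before the first dose. It does not rest on any assumed testing frequency or uptake. The number of hyperglycemia onsets that would fall in the gap cannot be estimated from the documents. No sample size, error rate or analysis depends on it. It is worth correcting because the correction is nearly free.

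**What to change.** In Section 6.1.2, encourage home glucose monitoring from the first rociletinib dose (Run-in Day 1 in Phase 1, C1D1 in Phase 2) through the end of Cycle 2. Hand out the tests at the Run-in Day 1 visit, when the diary card is already given (Section 8.4.6). Positive results then follow the existing route to a laboratory fasting glucose. Leave the laboratory schedule as it is.

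The cost is one wording change, one more week of home urine or blood testing for up to about 18 patients plus any run-in replacements, and an occasional unscheduled laboratory test. No scheduled visit is added.
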